## 6. GENERAL ANALYSIS CONSIDERATIONS

### 6.1. Data Reporting

The statistical analyses will be reported using summary tables, figures, and data listings. All output will be incorporated into Microsoft Word rich text format (.rtf) files, sorted and labeled according to the ICH recommendations, and formatted to the appropriate page size(s).

Laboratory units will be summarized and presented in the International System of Units (SI) and conventional units.

Individual subject data obtained from the electronic case report forms (eCRFs), external laboratory data, and any derived data (such as change from Baseline and percent change from Baseline) will be presented in data listings by subject. Data from all assessments, whether scheduled or unscheduled, will be listed by subject and visit. Unscheduled visits and visits occurring more than one day outside protocol defined window will not be included in the table summaries, excluding transient elastography measurements

The analyses described in this plan are considered a priori, in that they have been defined prior to database lock of the DB. Post hoc analyses will be labeled as such on the outputs and identified in the CSR.

Analyses and tabulations will be performed using SAS® Version 9.3 or higher. PK parameters will be estimated using Phoenix® WinNonlin® Version 6.3 or higher. The following processes will be employed to validate statistical outputs: analysis datasets, summary tables, and data listings will be verified through independent programming; graphical displays will be compared against supporting summary tables; and all outputs will undergo a senior-level statistical review. The process includes confirmation that statistically valid methods have been implemented and that all data manipulations and calculations are appropriate and accurate. Checks will be made to ensure accuracy, adherence to this SAP, consistency within tables, and agreement between tables and their corresponding data listings. Upon completion of validation/verification and quality review procedures, all documentation will be collected and filed in the study master file by the project statistician or designee.

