### **6.3.2. Missing Data**

Primary analysis of efficacy endpoints will utilize observed data only; missing values will not be imputed. A sensitivity analysis using a last observation carried forward (LOCF) approach may be considered. If performed, the LOCF imputation will replace any missing value from a DB post-Baseline visit with the last available non-missing value from a DB post-Baseline visit.

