## **9. EFFICACY ANALYSES**

The primary and secondary efficacy analyses will be based on the EE Population. Analyses on the ITT Population will only be performed if greater than 20% of ITT subjects are excluded in the EE Population. All analyses are to be carried out on observed data, as there are no imputations planned. The efficacy data are a result of the centralized, specialized nuclear magnetic resonance (NMR) lipoprotein assay and the central laboratory serum chemistry. All analyses of lipoprotein metabolism will include fasted samples only. For all lipoprotein concentration values, the serum chemistry panel results will be used. For particle size and particle concentration, the NMR lipoprotein assay results will be used. Sensitivity analysis may be performed with the NMR lipoprotein concentration results.

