## **11.6. Clinical Laboratory Evaluations**

Clinical laboratory evaluations during the DB are assessed at the central laboratory. The central laboratory reference/normal ranges will be used in determining whether a subject's value is above (H) or below (L) the reference/normal range. A listing of available laboratory reference/normal ranges for each laboratory parameter will be provided including age, sex, and values with units.

Quantitative hematology, coagulation, and serum chemistry laboratory parameters will be summarized by treatment group in SI and conventional units using arithmetic summary statistics as described in [Section 6.2.1](#) at Baseline and at each scheduled DB post-Baseline visit. Change from Baseline will also be summarized in the same manner. Re-tests or unscheduled visit results after first dose of investigational product in the DB will not be summarized but will be included in the data listings. Re-tests or unscheduled visit results prior to the administration time of the first dose in the DB will be included in the calculation of Baseline.

For laboratory test results that are below the quantifiable limits:

    Imputed laboratory result = (numeric portion of the result)  $\times$  0.9.

For laboratory test results that are above the quantifiable limits:

    Imputed laboratory result = (numeric portion of the result)  $\times$  1.1.

In addition, shift tables (ie, low-normal-high at Baseline versus low-normal-high at DB post-Baseline visit in a 3-by-3 contingency table) from Baseline to worst value, last value, and at each

scheduled DB post-Baseline visit will be provided for hematology, coagulation, and serum chemistry by treatment group. Worst post-Baseline value is defined as the most abnormal value.

Urinalysis results will not be summarized but will be provided in a data listing.

Listings of all laboratory values will flag values outside of the normal range as high (H) or low (L) and indicate whether or not a value is clinically significant (CS), based on Investigator judgment.

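### A valid fasting Week 16 LDL sample is discarded if it is unscheduled or more than one day outside the visit window, because the SAP has no rule assigning it to Week 16

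*SAP*

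**What the plan says.** Five provisions of the SAP act together on the Week 16 LDL endpoints (LDLc, LDLs, LDLpc).

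- **Section 6.1, visit rule:** "Unscheduled visits and visits occurring more than one day outside protocol defined window will not be included in the table summaries". The sentence ends with one exemption: "excluding transient elastography measurements".
- **Section 9, fasting and source:** "All analyses of lipoprotein metabolism will include fasted samples only". For LDLc, "For all lipoprotein concentration values, the serum chemistry panel results will be used"; particle size and particle concentration come from the NMR assay.
- **Section 11.6, re-tests of serum chemistry:** "Re-tests or unscheduled visit results after first dose of investigational product in the DB will not be summarized"; they are only listed. Before dosing the opposite holds: "Re-tests or unscheduled visit results prior to the administration time of the first dose in the DB will be included in the calculation of Baseline".
- **Section 6.3.2, missing data:** "Primary analysis of efficacy endpoints will utilize observed data only; missing values will not be imputed". As a fallback, "A sensitivity analysis using a last observation carried forward (LOCF) approach may be considered".
- **Sections 7.4 and 8.1, populations:** the EE Population, which is primary for efficacy, requires completion of the double-blind phase. Section 8.1 defines completion as having a non-missing LDL assessment at every visit it lists, Week 16 included.

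**The concern.** The fasting filter and the visit filter each remove samples, and nothing restores a usable one. A subject who arrives unfasted at Week 16 loses that sample under Section 9. If a fasting sample is then drawn and recorded as unscheduled, or falls more than one day outside the window, Section 6.1 removes it too. For LDLc, Section 11.6 points the same way. With no imputation, the subject contributes no Week 16 LDL value to the primary ANCOVA, although a fasting on-treatment value is in the database and in the listings.

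The cost is usable primary-endpoint data in arms of about 20. The subject may also be lost from EE at every visit if the discarded sample counts as missing for the completer definition. Section 6.1 recognises this kind of cost for elastography, an exploratory measure, but not for the primary endpoint.

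**Working it through.** **1. Following one subject through the rules.** Suppose the Week 16 sample is non-fasted and a fasting sample is drawn later, still on double-blind treatment.

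| Step | Rule | Result |
|---|---|---|
| Week 16 sample, non-fasted | Section 9 | Removed |
| Repeat recorded under Week 16, in window (or within the one-day grace) | Section 6.1 | Kept |
| Repeat recorded as unscheduled | Section 6.1; for LDLc also Section 11.6 | Listed only |
| Repeat beyond window plus one day | Section 6.1 | Listed only |
| Empty Week 16 value | Section 6.3.2 | Not imputed |
| Completer and EE status | Sections 8.1 and 7.4 | Possibly lost; the SAP does not say whether a discarded sample is missing |
| ITT ANCOVA by visit | Sections 9.1 and 6.2.3 | No Week 16 value |
| ITT repeated measures | Sections 9.1 and 6.2.4 | Earlier visits kept, redraw not used |

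A fasted Week 16 sample taken beyond window plus one day meets the same end without any redraw.

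**2. The plan's own figure.** Section 5 gives an increase of 22 mg/dL, SD 24, n = 20 per group, two-sided alpha 0.05 and power greater than 97.3%. A one-sample t-test has noncentrality (22/24) × √20 = 4.10 on 19 degrees of freedom. Its power is 97.29%, which matches the stated figure. The stated power is therefore for a within-group change. A two-sample t-test against placebo with the same difference and SD has power 80.6%.

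**3. Size of a loss.** The SAP gives no rate of non-fasted or out-of-window samples. I assume 2 to 4 of 20 per arm (10% to 20%). Half-width of the 95% CI for an arm's mean change = t(0.975, n−1) × 24/√n:

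| n per arm | Half-width (mg/dL) | Relative to n = 20 | Within-group power | Power against placebo |
|---|---|---|---|---|
| 20 | 11.23 | – | 97.3% | 80.6% |
| 18 | 11.93 | 11.93/11.23 = 1.06 | 95.6% | 76.2% |
| 16 | 12.79 | 12.79/11.23 = 1.14 | 92.8% | 70.9% |

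These are unadjusted single-arm figures. The SD is the Section 5 value for OCA 25 mg without atorvastatin, used here for scale only. If the ANCOVA residual variance is pooled over four arms, the widening is nearer √(20/18) = 1.05 and √(20/16) = 1.12.

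**The case against.** - **The rule is conventional and consistently applied.** Listing unscheduled post-dose results without summarizing them is common. Sections 6.1, 9.3.6, 11.6 and 11.7 agree with one another, so nothing is contradicted. This stands. The weakness is the combination with a fasting filter, no imputation and no mapping rule for the primary endpoint.
- **The protocol window is not shown.** A reader might infer that slightly late visits or any redraw are lost. The SAP does not support that: exclusion starts more than one day beyond a window of unknown width, and an in-window repeat recorded under Week 16 counts.
- **Strictness has a purpose.** Section 4 starts atorvastatin at Week 4, raises it at Week 8, allows titration after four further weeks, and offers open-label OCA after Week 16. An off-schedule sample may reflect another regimen. This stands and limits the remedy: a sample taken after such a change cannot be mapped back.
- **The Baseline contrast is weak.** A reader might call the different treatment of re-tests before and after dosing an inconsistency. It is not, because Section 6.3.1 defines Baseline as the last predose value, so earlier re-tests qualify naturally.
- **There is mitigation.** The repeated-measures ITT analysis is a commitment and keeps the subject's earlier visits. LOCF is only optional, and it could carry forward a value from a different atorvastatin regimen.
- **Section 6.1 speaks of table summaries, not model input.** The LS means are reported in those tables and Section 11.6 has a matching rule, so applying it to the ANCOVA is the natural reading. It remains a reading, and the SAP should settle it.

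**Conclusion.** The point holds in a limited form. As written, the SAP discards a valid fasting on-treatment LDL value when it is unscheduled or more than one day outside the window, leaves the Week 16 cell empty in the primary ANCOVA, and may remove the subject from EE.

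The size is modest and assumed. Losing 2 to 4 of 20 per arm widens the half-width by 6% to 14%, and within-group power stays at 92.8% or above. The exploratory contrasts with placebo lose more. The range treats every affected subject as otherwise usable; only those with a fasting sample before the next treatment change could be recovered.

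Two stronger inferences should be resisted. A reader might conclude that the loss differs by arm, for example because subjects with tolerability problems attend late; that is possible, but nothing in the SAP shows it. A reader might also conclude that the primary analysis becomes inadequate. The figures do not show that, and Section 6.2.8 treats intervals and p-values as descriptive.

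**What to change.** Before database lock, add a visit-mapping rule for the lipid endpoints:

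1. Define an analysis window around each target day, and use the fasting sample nearest that day, scheduled or unscheduled.
2. Close each window before the next treatment change set out in Section 4: start of atorvastatin, any change of atorvastatin dose, and the first LTSE dose.
3. State that this rule, rather than Section 6.1 or the re-test sentence in Section 11.6, governs the input to the lipid ANCOVA and repeated-measures models.
4. State that a mapped sample is a non-missing assessment for the completer definition in Section 8.1 and hence for EE in Section 7.4. The week list in Section 8.1 (2, 3, 4, 12, 16) should be reconciled at the same time with the clinic visits in Section 4 (2, 4, 8, 12, 16).
5. Keep the strict Section 6.1 rule as a sensitivity analysis.

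The cost is SAP wording, a small mapping step in programming and slightly more spread in sampling day. No new data are needed, since unscheduled results are already collected and listed.

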### 6.2. Data Analysis and Summaries

Data distribution characteristics will determine which analysis methods are most appropriate. If methods do not allow for parametric modeling assumptions to be met, then non-parametric methods will be implemented.

#### 6.2.1. Arithmetic Summaries

Continuous variables will be summarized with means, standard deviations (SDs), standard errors (SEMs) of the mean, medians, interquartile ranges (IQRs), minimums, and maximums.

#### 6.2.2. Categorical Methods

Categorical variables will be summarized by counts and percentage of subjects in corresponding categories. Percentages will be based on the number of non-missing assessments unless otherwise specified.

### 6.2.3. Analysis of Covariance

Analysis of covariance (ANCOVA) will be performed to provide least squares (LS) mean estimates and 95% confidence intervals (CIs) of the change and percentage change from Baseline at each DB post-Baseline visit. Model covariates will include the randomization stratification values (ie, pre-randomization fasted serum LDLc [ $\leq 125$  mg/dL or  $> 125$  mg/dL] and baseline fibrosis stage [stage 1, 2 or stage 3, 4]) and the Baseline value of the parameter being evaluated. The primary analysis will exclude the treatment by visit interaction term.

Example SAS code for the primary analysis is as follows:

ODS graphics on;

```
proc mixed data=ADEFF noclprint plots=residualpanel;
```

```
by visit;
```

```
class ldlcon fbstg trt;
```

```
model change=Baseline ldlcon fbstg trt / ddfm=kr;
```

```
lsmeans trt / cl diff alpha=0.05;
```

```
title1 "Linear Mixed Effects Model Based Estimates of XXXX Means by Visit";
```

```
title2 " Fixed Effects for Visit, Randomization Strata and Baseline as Covariates";
```

```
run;
```

```
ODS graphics off;
```

```
quit;
```

#### **6.2.4. Analysis of Covariance (Repeated Measures)**

Analysis of covariance (ANCOVA) with repeated measures will be performed to provide LS mean estimates and 95% CIs of the change and percentage change from Baseline at each DB post-Baseline visit. Model covariates will include the randomization stratification values (ie, pre-randomization fasted serum LDLc [ $\leq 125$  mg/dL or  $> 125$  mg/dL] and baseline fibrosis stage [stage 1, 2 or stage 3, 4]) and the Baseline value of the parameter being evaluated. This will include the treatment by visit interaction term. Example SAS code for the secondary analysis is as follows:

```
ODS graphics on;  
proc mixed data=ADEFF noclprint plots=residualpanel;  
    class subjid week ldlcon fbstg trt;  
    model change=trt week trt*week ldlcon fbstg Baseline/ ddfm=kr;  
    repeated week / subject=subjid type=un;  
    lsmeans trt*week / cl diff alpha=0.05;  
    title1 "Linear Mixed Effects Model Based Estimates of XXXX Means by Visit";  
    title2 " Fixed Effects for Visit, Randomization Strata and Baseline as Covariates, and  
        Treatment by Visit Interaction";  
run;  
ODS graphics off;  
quit;
```

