## **4. STUDY DESIGN AND PLAN**

This is a Phase 2, double-blind, randomized, placebo-controlled, multicenter study, evaluating the effects of OCA, and the subsequent addition of statin therapy, on lipoprotein metabolism in subjects with NASH with fibrosis stage 1 to 4, but no evidence of hepatic decompensation, in the DB phase, followed by an open-label LTSE phase to evaluate long term safety and efficacy.

Approximately 80 subjects with histological evidence of definite or probable NASH, who meet all inclusion and none of the exclusion criteria will be enrolled in the study. The histological evidence of definite or probable NASH will be based on the central read of a liver biopsy obtained no more than 1 year prior to randomization and a nonalcoholic fatty liver disease activity score (NAS) of 4 or greater. Subjects not using statin therapy (ie, statin-free) and statin-treated subjects may be enrolled. Statin-treated subjects will be required to stop statin treatment (after signing informed consent) for up to 5 weeks, including a 4-week statin washout period, prior to Randomization/Day 1.

Subjects will have a screening period of up to 5 weeks prior to Randomization/Day 1. At the Randomization (Day 1) Visit, subjects will be randomized in a 1:1:1:1 ratio to receive OCA 5 mg, OCA 10 mg, OCA 25 mg, or placebo, orally, once daily, for 16 weeks. Randomization will be stratified by the pre-randomization fasting serum LDLc ( $\leq$ 125 mg/dL or  $>$ 125 mg/dL) and baseline fibrosis stage (stage 1, 2 or stage 3, 4).

[figure not shown]
Subjects will attend on-site clinic visits at Weeks 2, 4, 8, 12, and 16 and will be contacted at Weeks 6, 10 and 14 to assess safety and treatment compliance. At the Week 4 Visit, all subjects will initiate treatment with atorvastatin at a dose of 10 mg once daily. At the Week 8 Visit, atorvastatin will be increased to 20 mg once daily (if 10 mg daily is tolerated), and continued for an additional 4 weeks. After 4 weeks of treatment at 20 mg, the atorvastatin dose may be titrated (up or down) as clinically indicated. The final visit during the DB phase will occur at Week 16, after which subjects may continue into the open-label LTSE.

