### **9.1. Primary Efficacy Analyses**

The primary efficacy analysis, changes in LDLc, LDLs, and LDLpc at Week 16 (end of DB) from Baseline will be summarized by treatment group, using the EE Population.

The observed values, change from Baseline, and percentage change from Baseline will be summarized by treatment group and visit using arithmetic summary statistics as described in [Section 6.2.1](#).

In order to provide estimates of the change from Baseline and corresponding 95% CI, the ANCOVA methods described in [Section 6.2.3](#) will be applied with change from Baseline as the dependent variable, including treatment group, and randomization stratification factor as fixed effects and Baseline as a covariate. The same analysis will be carried out using percentage change from Baseline as the dependent variable. Model fit will be assessed in order to determine the validity of the estimates. Estimates of LS means, SEs, and 95% CIs will be presented by treatment group.

The comparison of LDLc, LDLs, and LDLpc change from baseline and percentage change from baseline values between each active treatment group and placebo group at each DB post-Baseline visit will be performed as exploratory analyses. Estimates of the LS mean difference

between each active treatment group and placebo group, the SE of the difference, and 95% CI of the difference will be presented.

The relationship of OCA dose level and changes in LDLc will be explored using the Jonckheere-Terpstra (JT) test.

Sensitivity analysis for the primary efficacy analysis will be performed using the ITT Population using both the ANCOVA methods described in [Section 6.2.3](#) and the ANCOVA with repeated measures methods described in [Section 6.2.4](#).

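### The repeated-measures model in SAP 6.2.4 uses one Baseline slope for visits before and after atorvastatin starts; adding Baseline*week removes the misfit, which falls mainly on Week 4

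*SAP*

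**What the plan says.** Section 6.2.4 gives the repeated-measures model as "model change=trt week trt*week ldlcon fbstg Baseline/ ddfm=kr" with "repeated week / subject=subjid type=un". The text names one interaction only: "This will include the treatment by visit interaction term". Baseline and the two stratification factors each enter with one effect common to all weeks.

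Section 6.2.3 gives the primary model as "model change=Baseline ldlcon fbstg trt / ddfm=kr" and runs it separately by visit, so Baseline has its own slope each time.

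On design, section 4 states "Subjects will attend on-site clinic visits at Weeks 2, 4, 8, 12, and 16" and "At the Week 4 Visit, all subjects will initiate treatment with atorvastatin at a dose of 10 mg once daily". Weeks 2 and 4 are therefore off atorvastatin, and Weeks 8, 12 and 16 are on it.

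On use, section 9.1 states: "Sensitivity analysis for the primary efficacy analysis will be performed using the ITT Population using both the ANCOVA methods described in" section 6.2.3 and the repeated-measures model of 6.2.4. Appendix A lists both for LDL in the ITT Population. For HDL and VLDL, the repeated-measures tables are the only ITT tables it lists. Section 9.3.1 also names a repeated-measures ANCOVA for liver biochemistry but points to 6.2.3.

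**The concern.** A common slope says that a subject 10 mg/dL higher at Baseline has the same expected difference in change at Week 4 as at Week 16. That is hard to defend for absolute LDLc when a lipid-lowering drug is added to every arm in between. If the drug removes a roughly constant fraction of LDLc, subjects who start higher lose more mg/dL, and the slope steepens.

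Two things follow. The misfit goes into the residual variance and widens the confidence intervals. A chance difference in Baseline between arms is also adjusted with a slope that is wrong for a given visit, which leaves part of it in the treatment estimate.

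As a sensitivity analysis, the model then differs from the analysis it checks in a way nobody intended. If the two disagree, the forced slope is one more possible explanation alongside missing data.

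**Working it through.** **The plan's own figure.** The SAP gives no figure for this model. Its only relevant number is the power statement in section 5 (22 mg/dL, SD 24, 20 per group, two-sided 0.05). A within-group one-sample t test has noncentrality 22/24 × √20 = 4.10 and power 97.29%, which reproduces the stated 97.3%. A two-sample t test gives 80.6%. The figure does not depend on the 6.2.4 model; I use only its SD for scale.

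**Assumptions, not in the SAP.** Baseline LDLc SD 30-40 mg/dL; slope of post-Baseline LDLc on Baseline 0.75 before atorvastatin; proportional LDLc fall p of 20-45% on atorvastatin; residual correlation 0.3-0.7; residual SD 24 before atorvastatin, and afterwards either 24 or reduced in proportion. The SAP's 24 is the SD of change. With slope -0.25 and Baseline SD 30 the residual SD would be √(576 - 56.25) = 22.8, which makes the effects slightly larger.

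**True slopes of change on Baseline.**
- Weeks 2 and 4: 0.75 - 1 = -0.25.
- Weeks 8, 12 and 16: 0.75(1 - p) - 1, which is -0.40 at p = 20%, -0.5125 at 35% and -0.5875 at 45%.

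**What a common slope does.** With complete data and residual covariance S, the fitted slope tends to b = 1'S⁻¹β / 1'S⁻¹1. At visit t:
- shift in the arm difference = (β_t - b) × Baseline imbalance
- SE ratio = √(1 + (β_t - b)² × Var(Baseline) / σ_t²)

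**Case A: p = 35%, residual SD 24 throughout, equal correlation, Baseline SD 30.** The visits weigh equally, so b = (2 × -0.25 + 3 × -0.5125)/5 = -0.4075.
- Week 4: β - b = +0.1575, or +1.6 mg/dL per 10 mg/dL imbalance. SE ratio √(1 + 0.1575² × 900/576) = 1.019.
- Week 16: β - b = -0.105, or about -1.0 mg/dL per 10. SE ratio 1.009.

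**Case B: as A, but residual SD 0.65 × 24 = 15.6 on atorvastatin, correlation 0.5.** The weights become -0.0568 for each of Weeks 2 and 4 and 0.3712 for each of Weeks 8, 12 and 16. Then b = 0.0284 - 0.5707 = -0.542, which lies beyond the Week 16 slope.
- Week 4: +2.9 mg/dL per 10. SE ratio 1.065.
- Week 16: +0.3 mg/dL per 10, the same sign as Week 4. SE ratio 1.002.

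**Grid.** Seventy-two combinations were run, with correlation either equal at all visit pairs or decaying with time. Signs at Weeks 4 and 16 are opposite in all 36 cells with equal residual SD. Where the residual SD shrinks, they are opposite in 20 of 36 and the same in 16 of 36. The largest SE ratios are 1.29 at Week 4 and 1.10 at Week 16. Both come from the extreme cell: Baseline SD 40, p = 45%, correlation 0.7, residual SD down to 0.55 of its earlier value.

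**Simulation.** 80 subjects, stratified with "subjects will be randomized in a 1:1:1:1 ratio", five visits, unstructured covariance, 250 runs per scenario. Lowest and highest ratios across scenarios:

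| Visit | SE, common slope | SE with Baseline*week | Ratio |
|---|---|---|---|
| Week 4, low | 7.84 | 7.64 | 1.03 |
| Week 4, high | 8.54 | 7.53 | 1.13 |
| Week 16, low | 4.94 | 4.92 | 1.00 |
| Week 16, high | 5.06 | 4.92 | 1.03 |

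The shift per 10 mg/dL imbalance was +1.6 to +3.5 mg/dL at Week 4 and -1.0 to +0.9 at Week 16. After stratification the imbalance between two arms has SD about 7-8 mg/dL. At 7, Week 4 moves by 1.6 × 0.7 = 1.1 to 3.5 × 0.7 = 2.45 mg/dL; at 8 the upper end would be 2.8. Week 16 moves by at most 1.0 × 0.8 = 0.8 mg/dL. With no slope change, both SE ratios are 1.00 and there is no systematic shift.

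**The case against.** The case for leaving the model alone has real substance.

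- **The primary analysis is untouched.** It runs by visit. Section 9.1 also runs that by-visit ANCOVA in the ITT Population for LDL, so the picture before and after atorvastatin is available without this restriction in both populations. This stands and confines the point to the repeated-measures outputs.
- **Randomization keeps the contrasts unbiased on average.** The shift is conditional on chance imbalance, which stratifying on LDLc at 125 mg/dL limits. This stands.
- **Percentage change**, also a primary endpoint, should show little steepening if the lowering is proportional. This stands.
- **No slope change has been argued for HDL, VLDL or particle size.** The mechanism here is for LDLc. For the others the extra term is a precaution.
- **The code is labelled an example, and section 6.2.8 makes all intervals and p-values descriptive.** This lowers the stakes. But the text of 6.2.4 names no Baseline-by-week term either, and 9.1 promises a check of model fit without saying what follows from a bad one.
- **The repeated-measures model is not simply a stricter version of 6.2.3.** It uses partial data from subjects who drop out. This is true, and it is a reason to keep the model, not to keep the common slope.

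A reader might infer that Weeks 4 and 16 are always pushed in opposite directions. Case B shows otherwise: the sign depends on the residual covariance. A reader might also quote a 4 mg/dL error in the Week 16 minus Week 4 change in treatment effect. That takes slopes of -0.2 and -0.6 and a 10 mg/dL imbalance (0.4 × 10 = 4), and the SAP specifies no such contrast. With the slopes used here it would be 1.5-3.4 mg/dL per 10.

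**Conclusion.** The point holds as a modest, inexpensive improvement to the repeated-measures model. One Baseline slope across visits off and on atorvastatin is an implausible restriction for absolute LDLc, and 6.2.3 does not impose it. In the simulated scenarios the cost is an SE about 3-13% too large at Week 4 and 0-3% at Week 16. A 1-SD imbalance leaves about 1-2.4 mg/dL in the Week 4 difference and under 1 mg/dL at Week 16, against SEs of about 5-8. More extreme assumptions enlarge these figures; equal slopes remove them. All of them rest on slopes, SDs and correlations that the SAP does not state.

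The documents do not support a claim that the Week 16 primary result is compromised: the primary analysis does not use this model, and the effect at Week 16 is small even where the model is used.

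**What to change.** Before database lock, change the model statement in 6.2.4 to `model change = trt week trt*week ldlcon fbstg Baseline Baseline*week / ddfm=kr;` and name the Baseline-by-visit interaction in the text. With five visits this uses 4 degrees of freedom, from about 80 subjects. If the slopes are in fact equal, the SE ratio is 1.00, so nothing material is lost.

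The `ldlcon` and `fbstg` effects are also held constant over weeks. If the covariate adjustment is meant to match 6.2.3 fully, add `ldlcon*week` and `fbstg*week`, for 4 further degrees of freedom each.
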